Reference standard: disease status of a lesion will be defined by biopsy of lesions found on ^{68}Ga -RM2 and ^{68}Ga -PSMA-11 PET and from prior saturation prostate biopsy. Tissue samples will be evaluated for GRPr and PSMA expression as previously reported [1, 2] and results will be compared to imaging findings. For GRPr staining, immunohistochemistry will be performed using standard protocols with primary rabbit polyclonal antibody (OPA1-15619, 1:200 dilution; Affinity Bioreagents, Golden, Colorado). For PSMA, a rabbit polyclonal anti-PSMA antibody (D7I8E; Cell Signaling technology, #12815, 1:100 dilution) will be used following the manufacturer's immunohistochemistry protocol. We already successfully used

these, as shown on page 11.

Drs. [name] (clinical pathologist), [name] and [name] will perform all histopathological analyses. Clinical follow-up will be gold standard if biopsy cannot be done.

Test to be evaluated: All T1w, T2w, DWI and DCE MR images will first be analyzed and graded by two-board certified abdominal radiologists with subspecialty training in body MRI and extensive clinical experience in prostate MRI (Drs. [name] and [name]) using the PI-RADS version 2 scoring system, blinded to the clinical information and pathology. The PET images will be corrected using the attenuation data from the MRI scan, and Drs. [name] and [name] who already have extensive experience with ^{68}Ga -RM2 and ^{68}Ga -PSMA-11 from our clinical trials, will perform blinded and random interpretation of the PET scans. Areas of focally increased ^{68}Ga -RM2 and ^{68}Ga -PSMA-11 uptake above surrounding background will be considered positive for PC (**Figures 9 and 10**). This approach is based on recently published guidelines for standard image interpretation developed for ^{68}Ga -PSMA-11 image interpretation [90]. In addition, semi-quantitative measurements of tracer uptake (SUV_{\max}) will be recorded for each lesion.

Statistical Analysis: The following statistical considerations have the full support of a biostatistician ([name]) within the Department of Radiology, who has been specifically assigned to the project and can provide continuous support throughout the data collection and data analysis process. He has also carefully reviewed the study design and was fully involved in the writing of this grant proposal.

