Because there may be multiple lesions per-patient and an indefinite number of non-lesions, the primary analysis will be per-region. Each of the 12 regions will have gold-standard positive or negative information, as well as imaging positive or negative assessments. Predictive accuracy of PI-RADS composite score (mpMRI) and SUV_{\max} PET uptake values will be assessed by ROC analysis using univariable logistic regression for the presence of PC. Areas under the entire ROC curve, and partial area at fixed 90% specificity will be compared. Additional benefit of the other modalities over mpMRI alone will be tested by a multivariable logistic regression. All analyses will be adjusted for clustering within patient.

Statistical Power and Sample Size: Based on our clinical experience at Stanford, we expect an average of 2 PC-positive regions and 10 PC-negative regions per patient. Assuming mpMRI has sensitivity of 80% and specificity of 80-90% [91], a sample size of 1200 regions with 20% prevalence will provide 90% power at 5% error to demonstrate non-inferiority of a PET sensitivity of 90% at 80-90% specificity [62, 92, 93].

The per-lesion analysis will depend on the number of lesions found but will be similar. We will also explore whether specific imaging findings are especially accurate in detection of specific subtypes of PC or prostate regions (i.e., peripheral versus transitional zones). It may also be the case that

predictive failures in imaging may be associated with a particular subtype. Given the small sample, we acknowledge that this analysis will be exploratory.

10.2 Aim 2

Participants: Those enrolled in Aim 1.

Design: Patients will be scanned with both ⁶⁸Ga-RM2 PET/MRI and ⁶⁸Ga-PSMA-11 PET/MRI at six months after initiation of therapy. MRI and PET images will each be evaluated separately.

Outcome measures: Changes in MRI features and/or changes in radiopharmaceutical uptake in lesions will be recorded for each modality in each patient. Gold standard of response to treatment and of PFS will be based on standard clinical follow-up (PSA, imaging, tissue diagnosis including IHC stains for GRPr and PSMA)

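### Aim 1 compares the ROC area of an ordinal PI-RADS score with that of SUVmax, so equally accurate tests can differ in either direction depending on scale and on how lesion-free regions are scored

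*Combined protocol and SAP*

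**What the plan says.** All references are to section 10.1, Aim 1.

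- **Unit.** Under Statistical Analysis, "the primary analysis will be per-region", with 12 regions per patient. Each region has a gold-standard result "as well as imaging positive or negative assessments".
- **mpMRI marker.** MR images are graded "using the PI-RADS version 2 scoring system", and the composite score enters the ROC analysis. The documents do not give the number of levels, nor the score of a region without an MRI finding.
- **PET marker.** Under Test to be evaluated, focal "uptake above surrounding background will be considered positive for PC", which is a visual yes/no call. SUVmax "will be recorded for each lesion". No SUVmax is defined for a region without a lesion.
- **Method.** Predictive accuracy "will be assessed by ROC analysis using univariable logistic regression for the presence of PC". Then "Areas under the entire ROC curve, and partial area at fixed 90% specificity will be compared". The plan specifies no smoothed curve, tie rule or interpolation rule. Analyses are to be adjusted for clustering within patient, and added value over mpMRI is tested by multivariable logistic regression.
- **Hypothesis and power.** Both concern sensitivity: PET higher than mpMRI, sized on 90% against 80%.

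**The concern.** A logistic model with one predictor is a monotone transform of that predictor. It leaves the ranking, and hence the empirical ROC curve, unchanged. Regions tied on PI-RADS stay tied, and the curve is a few points joined by straight lines. A concave curve loses area when it is replaced by chords, and the longest chord is the one running to (1,1) from the lowest cut point. A marker measured on a continuous scale in every region loses nothing. A marker recorded only where a lesion is visible has a long chord of its own. The measured difference in area therefore mixes accuracy with scale and with a data convention that the plan does not state.

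The partial area has a second problem. A fixed specificity of 90% is a point and has no width, so the statistic cannot be programmed as worded. If no PI-RADS cut-off falls at 90%, mpMRI's value there is interpolated.

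At stake is whether the Aim 1 comparison of PET with mpMRI reflects diagnostic accuracy. It could favour one modality when the two are equally accurate.

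**Working it through.** **The plan's own figure.** No AUC figure is given; the only one is 90% power at 5% error for sensitivity. 1200 regions × 20% = 240 positive regions. For 80% against 90%, unpaired and without clustering, power is 92.5% one-sided and 86.8% two-sided. With 2 of 12 regions positive (200 regions) it is 87.8% and 80.2%. The stated 90% lies within this range, but margin and sidedness are not given. Nothing in it sizes a comparison of areas.

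**Model (assumed).** Negative regions N(0,1), positive regions N(d,1), the same for both tests, with d = z(0.80) + z(specificity). The operating points are the plan's mpMRI values. Smooth AUC = Φ(d/√2). At 80% specificity d = 0.842 + 0.842 = 1.683 and AUC = Φ(1.190) = 0.883.

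**PI-RADS (assumed cut points).** With f = 1 − specificity, cuts lie at false-positive rates f, 0.5f and 0.15f (four levels: MRI-negative regions share one category), plus 2.5f for five levels. Sensitivity at each cut is Φ(d + z(FP)).

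At 80% specificity the points are (0.03, 0.422), (0.10, 0.656), (0.20, 0.800), and (0.50, 0.954) for five levels.

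- Four levels, trapezoids: 0.0063 + 0.0377 + 0.0728 + 0.7200 = 0.837.
- Five levels: the last term becomes 0.3 × (0.800 + 0.954)/2 + 0.5 × (0.954 + 1)/2 = 0.2631 + 0.4885, giving 0.868.

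**SUVmax for visible lesions only.** Positivity is set at the same specificity and other regions are tied at the bottom. The smooth area up to FP 0.20 is 0.1215; adding the chord, 0.8 × (0.8 + 1)/2 = 0.7200, gives 0.842.

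| Specificity | SUVmax in all regions | PI-RADS, 5 levels | PI-RADS, 4 levels | SUVmax, lesions only |
|---|---|---|---|---|
| 80% | 0.883 | 0.868 | 0.837 | 0.842 |
| 85% | 0.908 | 0.892 | 0.855 | 0.858 |
| 90% | 0.933 | 0.913 | 0.871 | 0.874 |

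**PET minus mpMRI, equal true accuracy.**

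- SUVmax in all regions: +0.015 to +0.020 against five levels; +0.046 to +0.062 against four. Three other plausible five-level cut-point sets give +0.013 to +0.033.
- SUVmax for lesions only: +0.003 to +0.005 against four levels; −0.027 to −0.039 against five, which favours mpMRI. Across the other five-level sets, including PET thresholds that differ from the mpMRI operating point, the range is −0.004 to −0.076.

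**How often a test is misled.** Simulation of 100 patients × 12 regions, 2 positive each, 600 runs per setting, patient-clustered DeLong-type test at two-sided 5%, assumed intraclass correlation 0.1 and between-test correlation 0.4.

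- SUVmax in all regions, five levels: PET falsely favoured in 15-48% of trials.
- SUVmax in all regions, four levels: 77% at 80% specificity and 98% at 90%.
- Both markers continuous (control): about 3% in that direction.
- SUVmax for lesions only, five levels, matched specificity: mpMRI falsely favoured in 9-33% of trials at 80% and 62-84% at 90%; PET in under 1.5%.

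**Partial area, FP 0 to 0.10.** At 80% specificity the smooth value is 0.0478 and PI-RADS gives 0.0063 + 0.0377 = 0.0440, 7.9% lower. At 90% it is 0.0638 against 0.0611, 4.2% lower. Four and five levels coincide here because the extra cut lies outside the range. Other cut points can lose more: a well-spread set loses 0.0056/0.0478 = 11.7% and 0.0086/0.0638 = 13.5%. Lesion-only SUVmax loses nothing in this range if its positivity threshold is at or below 90% specificity.

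**The case against.** The strongest reply is that the plan does not stake Aim 1 on AUC. It makes the region the primary unit but does not name the area as the deciding statistic; the hypothesis and power are about sensitivity, and every region also gets a positive/negative call that has no scale problem. Added value is tested separately, and the registered outcomes in section 10.3 are participant counts. A fitted ordinal ROC is not excluded. This stands as a limit on the consequences. Yet the area comparison is the only head-to-head statistic named for mpMRI against PET, and no fitted curve is specified.

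A second reply is that the result depends on assumed levels and cut points. That is correct, and it is why ranges are given.

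A reader might infer the stronger claim that the analysis has a built-in, one-way bias towards PET. The documents do not support it for the full AUC. That claim needs SUVmax in all 1200 regions, whereas the plan records it for each lesion. With other regions tied, the difference nearly vanishes or reverses. The very high rates of false PET advantage also need MRI-negative regions merged into one category, which the plan does not state.

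The planned clustering adjustment is no defence: the simulated test was clustered, and clustering changes the variance, not the bias.

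**Conclusion.** The concern holds in conditional form. As written, the comparison can give a scale-driven difference in AUC between equally accurate tests, and unstated conventions decide its direction.

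- **SUVmax in every region:** five-level PI-RADS reads about 0.01-0.03 too low, or 0.05-0.06 if MRI-negative regions share a category. PET is falsely favoured in roughly 15-48% of trials with five levels.
- **SUVmax for visible lesions only, others tied:** about zero against four levels; about 0.03-0.04 in favour of mpMRI against five.
- **Partial area over specificity 90-100%:** PI-RADS 4-8% too low under the main cut points and more under some others. The direction is steadier here, but the plan gives no range.

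The binormal form, level counts, cut points, intraclass correlation and between-test correlation are assumptions, not figures from the documents. The documents do not support calling the plan biased towards PET, or saying that AUC alone decides Aim 1. They do support saying that the named comparison does not match the hypothesis and is not fully defined.

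**What to change.** 1. Make the deciding Aim 1 comparison the paired difference in per-region sensitivity, clustered by patient, with specificity reported alongside. Use the positive/negative calls already planned for all 12 regions, and prespecify the PI-RADS cut-off that makes a region mpMRI-positive.
2. If a comparison at matched specificity is wanted, first define a region-level SUVmax for all 12 regions, read from the existing images. Use a patient-level bootstrap that re-estimates the SUVmax cut-off in each resample.
3. Keep AUC as descriptive, with both modalities handled the same way (a smooth or ordinal-regression ROC), and state the value given to a region without a finding.
4. Define the partial area as specificity 90-100%.

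Items 1, 3 and 4 cost SAP wording and routine programming. Item 2 needs some extra measurement on existing scans but no new imaging. The drawback is that a single operating point uses less of the curve than AUC does.

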5. Approximately 45 to 60 minutes after the radiopharmaceutical IV administration, data acquisition will begin in the pelvic region and move toward the head. First, localizer MRI scans will be performed to define the table positions. After correct positioning of the spatial acquisition windows is ensured, the combined PET/MRI acquisition will be initiated with 3 to 5 table positions at a 2 to 4 minute acquisition time per table position. Only MR sequences required for attenuation correction of PET data will be acquired.
6. Vital signs (heart rate, blood pressure) will be recorded again at the completion of the study.
7. Participants will be contacted at 24 to 72 hours following the scan in order to capture potential occurring Adverse Events.

The above will be repeated approximately 6 months after HIFU or HDR local treatment, prior to standard of care biopsy to evaluate for residual disease in the prostate.

Objectives of the Study

Primary Objectives

- To demonstrate that ⁶⁸Ga-RM2 and ⁶⁸Ga-PSMA-11 PET/MRI can detect additional cancers over mpMRI.
- To demonstrate that ⁶⁸Ga-RM2 and ⁶⁸Ga-PSMA-11 PET/MRI can assess changes in response to treatment and predict PFS at 24 months.

Secondary Objective

- None

Endpoints

Primary Endpoints

- Number of participants with assessable additional prostate cancer lesions over mpMRI
- Number of participants with assessable pre- and post-treatment uptake in response to HIFU or HDR local therapy

Secondary Endpoint

- None

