9.2 Data Management Plan

The CRFs will be stored in a locked office in the Nuclear Medicine clinic. Records will be kept using OnCore.

During the clinical investigation, the Protocol Director will evaluate the progress of the trial, including periodic assessments of data quality and timeliness, participant recruitment, accrual and retention, participant risk versus benefit, performance of trial sites, and other factors that can affect study

outcome. Monitoring of the trial will occur every 8 weeks and a record of monitoring activities will be maintained by the study team.

The Stanford Cancer Institute Data and Safety Monitoring Committee (DSMC) will audit study related activities to determine whether the study has been conducted in accordance with the protocol, local standard operating procedures, FDA regulations, and Good Clinical Practice (GCP). This may include review of regulatory binders, case report forms, eligibility checklists, and source documents. In addition, the DSMC will regularly review serious adverse events and protocol deviations associated with the research to ensure the protection of human subjects. Results of DSMC audits will be communicated to the IRB and the appropriate regulatory authorities at the time of continuing review, or in an expedited fashion, as needed.

10. Statistical Considerations and Evaluation of Results

10.1 Aim 1

Participants: 100 patients with low- or intermediate-risk prostate cancer, as described in the inclusion/exclusion criteria.

Design: Patients will have both ^{68}Ga -RM2 and ^{68}Ga -PSMA-11 PET/MRI, including mpMRI. mpMRI and PET images will each be evaluated separately. For each of the 12 prostate regions, between 1-3 imaging-positive samples will be taken, and 1 sample will be taken from each imaging-negative region.

Outcome measures: Number and location of lesions will be recorded for each modality in each patient. Gold standard will be based on the biopsy of lesions found on ^{68}Ga -RM2 and ^{68}Ga -PSMA-11 PET and prior systematic prostate biopsy, including IHC stains for GRPr and PSMA.

Hypothesis: ^{68}Ga -RM2 and ^{68}Ga -PSMA-11 PET/MRI sensitivity, either alone or in combination, will be higher than that of mpMRI alone.

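### The regression assigned to PET's added benefit can be significant when PET finds no more mpMRI-missed cancers than chance, so by itself it does not support the additional-cancers objective

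*Combined protocol and SAP*

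**What the plan says.** The first primary objective (Section 2.5) is that the two PET/MRI scans "can detect additional cancers over mpMRI". The Aim 1 hypothesis (Section 10.1) is that PET/MRI sensitivity, "either alone or in combination, will be higher than that of mpMRI alone".

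Under Statistical Analysis in Section 10.1, "the primary analysis will be per-region", with 12 regions per man and adjustment for clustering. Two inferential steps follow:

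- Univariable logistic models for PI-RADS and for SUVmax, after which "Areas under the entire ROC curve, and partial area at fixed 90% specificity will be compared".
- For added value: "Additional benefit of the other modalities over mpMRI alone will be tested by a multivariable logistic regression". The terms, any interaction and the test statistic are not given.

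The power statement concerns non-inferiority of PET sensitivity (90%, against 80% for mpMRI) and gives no margin. McNemar tests appear only in Section 10.2, for Aim 2. The endpoints in Sections 2.5 and 10.3 count participants with assessable results, so they test nothing about added detection.

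On sampling, the Design paragraph of 10.1 allows one to three samples in an imaging-positive region, while "1 sample will be taken from each imaging-negative region".

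**The concern.** A cancer that PET adds to mpMRI lies, by definition, in a region that mpMRI called negative. The regression, on its natural reading, pools these regions with the mpMRI-positive ones and gives PET a single coefficient. PET can earn a large coefficient by separating true from false positives among regions that mpMRI has already marked. That is a real gain in accuracy, but it is not additional detection.

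The plan names no other analysis of benefit over and above mpMRI. The trial could therefore report a significant added benefit, and have it read as proof of additional cancers, when PET found missed cancers no more often than it marked benign tissue.

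**Working it through.** **Inputs from Section 10.1.** 100 men × 12 regions = 1200 regions. Two positive regions per man give 200 (16.7%); the power statement's 20% prevalence gives 240. mpMRI sensitivity is 80% and specificity 80–90%. Cancers missed by mpMRI: 0.20 × 200 = 40, or 0.20 × 240 = 48.

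**The plan's own power figure.** For PET 90% against mpMRI 80% with margin m, power = Φ[(0.10 + m)/√((0.9×0.1 + 0.8×0.2)/n) − z]. With m = 0 and one-sided 5%:

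- n = 200: 0.10/√(0.25/200) = 2.828, less 1.645 = 1.18, so 88.2%.
- n = 240: 92.7% (87.3% at one-sided 2.5%).

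The stated 90% cannot be confirmed without the margin, sidedness and correlation. It is in any case not the power of the added-value regression.

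**Expected counts under a constructed null.** Take mpMRI specificity 85%. Assume PET is positive in 90% of cancers in mpMRI-positive regions and in 15% of all other regions, including the missed cancers.

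| | PET+ cancer | PET− cancer | PET+ benign | PET− benign | Odds ratio |
|---|---|---|---|---|---|
| mpMRI-positive (310) | 144 | 16 | 22.5 | 127.5 | 51 |
| mpMRI-negative (890) | 6 | 34 | 127.5 | 722.5 | 1 |

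In mpMRI-negative regions the cancer rate is 6/133.5 = 4.5% if PET-positive and 34/756.5 = 4.5% if PET-negative: no added detection. A single common odds ratio across both rows (Mantel–Haenszel) is (144×127.5/310 + 6×722.5/890)/(22.5×16/310 + 127.5×34/890) = 64.10/6.03 = 10.6. The pooled association is strong, and all of it comes from the first row.

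**Simulated rejection rates with PET at chance among missed cancers** (cluster-robust standard errors, one-sided 5% assumed, 400 trials per setting, specificity 80–90%):

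- Pooled PET term: 100% when PET is positive in 90% or 50% of cancers in mpMRI-positive regions, and 59–98% when it is positive in 30%. A repeat run spanned 62–100% overall.
- The same model within mpMRI-negative regions: 4–7%.

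A separate set of runs (two-sided 5%, positive direction counted) gave 100% for the pooled term in all 16 combinations of prevalence, specificity, false-positive rate and clustering. It gave 89.5% when PET was only weakly informative in mpMRI-positive regions (70% of cancers against 50% of benign). With PI-RADS- and SUV-like scores the figures were 82–100% pooled against 1–2% restricted. When PET was uninformative everywhere, the pooled term was positive and significant in 2.3%, its nominal level.

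**When PET does find missed cancers** (PET false-positive rate 15%, 90% of cancers in mpMRI-positive regions, clustering ignored in the restricted test):

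| PET-positive among missed cancers | Overall PET sensitivity | Pooled term | mpMRI-negative only | McNemar on sensitivity, favouring PET |
|---|---|---|---|---|
| 15% (chance) | 0.72 + 0.2×0.15 = 75% | 100% | 4% | 0% |
| 30% | 78% | 100% | 69% | 0.2% |
| 40% | 80% | 100% | 98% | 2.2% |
| 50% | 82% | 100% | 99.5% | 8% |

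The pooled term does not tell these rows apart. The head-to-head test does not see the 40% row, where PET finds 16 of 40 missed cancers but has the same overall sensitivity as mpMRI.

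**Unequal sampling.** With an assumed 50% chance that one core detects cancer in a cancerous region, one core finds 50% and three find 1 − 0.5³ = 87.5%; at 80% per core the figures are 80% and 99.2%. If a PET-positive, mpMRI-negative region counts as imaging-positive, it may receive up to three cores and its PET-negative counterpart one. Under the same null, with per-core detection of 50–80%, the restricted test then rejected in about 13–37% of trials.

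**The case against.** The strongest counter-argument is that the regression does not carry the objective alone. The hypothesis is about sensitivity, and 10.1 also compares full and partial AUC. A true PET sensitivity of 90% against 80% means 180 cancers detected, of which at most 160 are in mpMRI-positive regions, so PET must find at least 20 of the 40 missed. In the null runs the head-to-head evidence pointed away from PET: its overall sensitivity was 74–76% or lower against 80%, and a one-sided paired sensitivity test favoured PET in essentially none of them. This stands. A reader might infer that the error rate for the first primary objective is uncontrolled; for PET alone, the documents do not support that.

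The head-to-head comparison does not, however, address the in-combination part of the hypothesis, and it has little power when PET finds different cancers without a higher overall sensitivity.

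Two further points also stand. The main-effects form is inferred, because the plan says only that the model is multivariable. And chance-level PET among missed cancers is a constructed case. Section 2.1 says mpMRI misses about 20% of index lesions, and nothing in the documents shows that PET and mpMRI mark the same regions. The case shows what the test cannot rule out, not what is expected.

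Finally, a restricted test that ignores the sampling rule would itself be biased towards PET. That is a reason to adapt the remedy, not to drop it.

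**Conclusion.** The concern holds in limited form. The one analysis assigned to PET's benefit in addition to mpMRI can be significant in most or all trials (62–100% simulated) when PET only sorts true from false mpMRI positives. It therefore does not by itself support a claim of additional cancers.

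The figures rest on PET rates by mpMRI stratum, which the documents do not give, on a main-effects reading of the model, and on an assumed one-sided 5% level. Two stronger statements go too far: that the term is always significant (it keeps its level if PET is uninformative everywhere), and that no other planned comparison bears on the objective. The gap is in the combination claim and in the wording of the conclusion. It should be closed before analysis.

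**What to change.** In Section 10.1:

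- Write out the pooled model and keep it as a measure of overall added accuracy.
- Base the additional-cancers statement on the PET effect within mpMRI-negative regions, through a PET × mpMRI-status interaction evaluated at mpMRI-negative or the clustered model restricted to those regions.
- Prespecify one PI-RADS cut-off for calling a region negative (10.1 states none) and a multiplicity rule for the two tracers.
- Define the reference result for this test from an equal number of samples per region, for example one prespecified sample plus the prior systematic biopsy. Use the all-samples result as a sensitivity analysis.
- Report the PET-positive rate in cancerous and in benign mpMRI-negative regions, and both sensitivity and specificity of mpMRI plus PET against mpMRI. Sensitivity alone misleads. With a 10–20% PET false-positive rate, an either-positive rule raises it by chance from 80% to 0.80 + 0.20×0.10 = 82% up to 0.80 + 0.20×0.20 = 84%.

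The cost is SAP wording, one more model and a record of which sample is the prespecified one; no new data are needed. The downside is precision. The test rests on about 40 missed cancers (48 at 20% prevalence). At the assumed 50–80% per-core detection, a single sample would confirm only 20–32 of the 40 before the prior biopsy is added. The restricted-test power shown above assumes a perfect reference result, so it should be recalculated under the chosen definition.

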10.3 Study Outcomes (ClinicalTrials.gov)

Primary Outcomes

Title: ⁶⁸Ga-RM2 and ⁶⁸Ga-PSMA-11 PET/MRI can detect additional cancers over mpMRI

Description: Detection of PC lesions will be assessed by ⁶⁸Ga-PSMA-11 and ⁶⁸Ga-RM2 PET scans. The outcome is the number of participants without dispersion, by randomization schedule, for which an assessment of PET-based PC lesions is successfully obtained.

Timeframe: 60 months

Safety outcome: No

Title: ^{68}Ga -RM2 and ^{68}Ga -PSMA-11 PET/MRI can assess changes in response to treatment and predict PFS at 24 months

Description: Therapeutic response to HDR will be assessed by ^{68}Ga -PSMA-11 and ^{68}Ga -RM2 PET scans. The outcome is the number of participants without dispersion, by randomization schedule, for which an assessment of PET-based therapeutic response to HDR is successfully obtained.

Timeframe: 84 months

Safety outcome: No

Secondary Outcome

None.

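### Aim 1 hypothesises higher sensitivity for PET/MRI than mpMRI, but its section 10.3 outcome is a feasibility count and its power statement is labelled non-inferiority with no margin, sidedness or matching test

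*Combined protocol and SAP*

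**What the plan says.** The first primary objective in section 2.5 is to show that PET/MRI finds cancers beyond those seen on mpMRI. The Aim 1 hypothesis in section 10.1 is that "PET/MRI sensitivity, either alone or in combination, will be higher than that of mpMRI alone". The parts of the plan that should deliver this read as follows.

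- **Endpoint, section 2.5:** "Number of participants with assessable additional prostate cancer lesions over mpMRI". This refers to mpMRI but does not require biopsy confirmation.
- **Primary outcome, section 10.3:** "The outcome is the number of participants without dispersion, by randomization schedule, for which an assessment of PET-based PC lesions is successfully obtained". The title of this outcome mentions mpMRI; the quantity counted does not.
- **Primary analysis, section 10.1:** per region, 12 regions per patient, using PI-RADS and SUVmax. "Areas under the entire ROC curve, and partial area at fixed 90% specificity will be compared". Then: "Additional benefit of the other modalities over mpMRI alone will be tested by a multivariable logistic regression". And: "All analyses will be adjusted for clustering within patient".
- **Power, section 10.1:** "a sample size of 1200 regions with 20% prevalence will provide 90% power at 5% error to demonstrate non-inferiority of a PET sensitivity" of 90%, with mpMRI at 80% and specificity of 80-90%. No margin, sidedness or design effect is given. The preceding sentence says "we expect an average of 2 PC-positive regions and 10 PC-negative regions per patient".

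Section 10.2 (Aim 2) does state one-sided 5% error and names McNemar tests. Section 10.1 does neither.

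**The concern.** The hypothesis is a superiority claim about sensitivity. The section 10.3 count would be complete if every scan were readable, even if PET found no biopsy-proven cancer that mpMRI had missed. A non-inferiority conclusion would not establish higher sensitivity, and without a margin the test cannot be carried out as labelled. The analysis paragraph compares ROC areas and tests added benefit by regression, while the sample size is justified by a difference in sensitivity for which no test is named. The hypothesis also allows RM2, PSMA-11 or the combination to succeed, with no testing order.

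At stake is whether Aim 1 could be reported as complete without answering its question, and whether the deciding analysis is fixed before the data are seen. A second matter is whether the 90% power survives the plan's own statements about positive regions and clustering.

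**Working it through.** **1. Reproducing the plan's figure.** Inputs from section 10.1: sensitivities 0.80 and 0.90, 5% error, 90% power, and 1200 × 0.20 = 240 positive regions. Treat this as one-sided superiority with independent, unpaired regions:

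n = [1.645·√(2·0.85·0.15) + 1.2816·√(0.80·0.20 + 0.90·0.10)]² / 0.10² = (0.8306 + 0.6408)² / 0.01 = 216.5, so 217.

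With continuity correction, (217/4)·[1 + √(1 + 4/(217·0.10))]² = 236.6, so 237. The plan has 240, so the 90% reproduces on this reading. The two-sided equivalents are 266 without correction and 286 with it.

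**2. Does non-inferiority fit?** With true values of 90% and 80% and 240 positives, the margin that gives exactly 90% power is (z₁₋α + 1.2816)·√(0.25/240) − 0.10. That is −0.6 points at one-sided 5% and +0.5 points at one-sided 2.5%. A margin of about zero is superiority, so the label looks wrong rather than the number.

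**3. Number of positive regions.** 2 of 12 is 16.7%, and 100 × 2 = 200. The 20% used for power gives 240, or 2.4 per patient, which may simply have been rounded to 2.

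**4. Paired superiority without clustering.** Both modalities are read in the same regions, so power depends on the proportion of positive regions where they disagree (pd):

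Power = Φ[(0.10·√n − z·√pd) / √(pd − 0.01)]

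The plan's rates bound pd between 0.90 − 0.80 = 0.10 and 0.20 + 0.10 = 0.30. Independent errors give 0.9·0.2 + 0.1·0.8 = 0.26. Where pd falls within the bounds is an assumption.

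| pd | n = 240, one-sided | n = 200, one-sided | n = 200, two-sided |
|---|---|---|---|
| 0.10 | >99.9% | 99.9% | 99.6% |
| 0.18 | 98% | 96% | 92% |
| 0.26 | 92% | 88% | 80% |
| 0.30 | 89% | 83% | 74% |

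Example, n = 200, pd = 0.26, one-sided: (1.4142 − 1.645·0.5099)/0.5 = 1.151, and Φ = 0.875. Two-sided at 240 and pd 0.26 gives 86%. One-sided, 90% power holds up to pd = 23.8% at 200 positives and 28.5% at 240.

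**5. Clustering.** Assume exactly 2 positive regions per patient and an intraclass correlation (ICC) of the paired PET-minus-mpMRI differences. The design effect is 1 + (2 − 1)·ICC.

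| ICC (assumed) | Effective n (200 / design effect) | pd 0.26, one-sided | pd 0.18, one-sided |
|---|---|---|---|
| 0.2 | 200/1.2 = 166.7 | 82% | 92% |
| 0.5 | 200/1.5 = 133.3 | 74% | 87% |

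**6. Outcome against hypothesis.** The hypothesis needs three elements: a PET reading, an mpMRI reading and tissue status. The section 10.3 count uses only the first. The section 2.5 endpoint uses the first two. The per-region analysis in section 10.1 uses all three, but is not listed as an outcome in either place.

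**The case against.** The best defence is that section 10.3 carries registry wording, while section 10.1 names the per-region analysis as primary and gives each region both imaging calls and reference status. Partial area at 90% specificity reflects sensitivity in the high-specificity range, close to the 80-90% specificity in the power statement. All of this stands, and it means the analysis and the power are related. They are still not the same quantity: no test of the sensitivity difference is named, and section 10.3 remains the protocol's own list of primary outcomes.

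Stronger readings are tempting, but the documents do not support them.

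- **A reader might infer that the 90% is an error or that the trial is underpowered.** The figure reproduces at 240 positives, and even at 200 it is exceeded if discordance is below about 24% and regions are independent. The plan gives neither discordance nor ICC.
- **A reader might infer that an ineffective PET could readily pass as non-inferior.** How often depends entirely on a margin that the documents do not contain, and the sample size fits a margin near zero.
- **A reader might infer that the reference standard is contradictory.** Section 10.1 samples every region and says all 12 have reference information. The definition based on PET lesions and prior biopsy speaks of lesions, and a separate per-lesion analysis is planned. Two units of analysis is a fair reading; the text should say so.

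**Conclusion.** The concern holds as a mismatch that must be corrected. The section 10.3 count cannot show that the objective was met. The power statement's label contradicts the hypothesis and lacks a margin and sidedness, and the difference it powers has no named test.

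The power figure is a lesser matter. It is right under one-sided, unpaired, independent superiority at 240 positives. At the plan's own 2 positives per patient, without clustering and at 26% discordance, it becomes 88% one-sided or 80% two-sided. With the assumed ICC of 0.2 to 0.5 it is 82% to 74% one-sided. At 18% discordance the one-sided figures are 96% unclustered and 92% to 87% clustered. These results rest on normal approximations and on assumed discordance, ICC and a fixed 2 positives per patient. A shortfall is possible, not shown.

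**What to change.** 1. In sections 2.5 and 10.3, make the Aim 1 primary outcome the per-region comparison of PET with mpMRI against the biopsy reference. Keep the count of assessable participants as a feasibility measure. The number of participants with a biopsy-confirmed region that is PET-positive and mpMRI-negative can be supportive.
2. In section 10.1, replace non-inferiority with superiority and state sidedness.
3. Match the primary test to the power. Either use a cluster-adjusted paired test of sensitivity, with a fixed PI-RADS cut-off and specificity held comparable (for example at the plan's 90%), or keep partial area at 90% specificity as primary and power that. Sensitivity alone should not decide, because calling more regions positive raises it. Give a testing order for RM2, PSMA-11 and the combination.
4. Restate power at 200 positive regions over stated discordance and ICC values, and reconcile 20% with 2 of 12.
5. State that the per-region reference is the all-region sampling in the section 10.1 design, and that the PET-lesion definition applies to the per-lesion analysis.

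The cost is protocol and registry wording. It adds no patients or scans, and no biopsies beyond the sampling already described. No larger sample is required. The downside is that the stated power may look less favourable, and later tests in the order count only if earlier ones succeed.
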